# 5.2.6.1.2 Serious adverse event

A SAE is defined as any AE, which fulfils at least one of the following criteria:

- Results in death.
- Is life-threatening, which refers to an event in which the participant was at risk of death at the time of the event; it does not refer to an event that hypothetically might have caused death if more severe.
- Requires inpatient hospitalisation or prolongation of existing hospitalisation.
- Results in persistent or significant disability or incapacity.
- Is a congenital anomaly/birth defect.
- Is deemed serious for any other reason if it is an important medical event when based on appropriate medical judgement which may jeopardise the participant and may require medical or surgical intervention to prevent one of the other outcomes listed in the above definitions. Examples of such events are intensive treatment in an emergency room or at home for allergic bronchospasm, blood dyscrasias or convulsions that do not result in hospitalisation or development of dependency or abuse.

For Japan only: an event that possibly leads to disability will be handled as "deemed serious for any other reason" and, therefore, reported as an SAE.

# 5.2.6.1.3 AEs considered "Always Serious"

In accordance with the European Medicines Agency initiative on Important Medical Events, Boehringer Ingelheim has set up a list of AEs, which by their nature, can always be considered to be "serious" even though they may not have met the criteria of an SAE as defined in Section 5.2.6.1.2. The latest list of "Always Serious AEs" can be found in the eDC system. A copy of the latest list of "Always Serious AEs" will be provided upon request. These events should always be reported as SAEs as described in Section 5.2.6.2.

Cancers of new histology and exacerbations of existing cancer must be classified as a serious event regardless of the time since discontinuation of the drug and must be reported as described in Section 5.2.6.2, subsections "AE Collection" (Section 5.2.6.2.1) and "AE reporting to sponsor and timelines" (Section 5.2.6.2.2).

Page 86 of 177

Proprietary confidential information © 2023 Boehringer Ingelheim International GmbH or one or more of its affiliated companies

# 5.2.6.1.4 Adverse events of special interest

The term "adverse event of special interest" (AESI) relates to any specific AE that has been identified at the project level as being of particular concern for prospective safety monitoring and safety assessment within this trial, e.g. the potential for AEs based on knowledge from other compounds in the same class. AESIs need to be reported to the sponsor's Pharmacovigilance Department within the same timeframe that applies to SAEs; please see Section 5.2.6.2.2.

# The following are considered as AESIs:

Systemic hypersensitivity including infusion reaction and anaphylactic reaction
Any suspicion of severe infusion reaction systemic/hypersensitivity reaction and of any
potential cases of anaphylaxis should be defined and assessed using the criteria discussed in
the statement paper from Sampson HA (Appendix 10.20 [R11-4890]), see Section 4.2.1 for
"Other treatments and emergency procedures".

Severe infections (according to CTCAE grading in Section 15 of the ISF) (See Section 4.2.1 for "Other treatments and emergency procedures")

# Opportunistic and mycobacterium tuberculosis infections

These include pneumocystis jirovecii, BK virus disease including PVAN, CMV, post-transplant lymphoproliferative disorder (EBV), progressive multifocal leucoencephalopathy, bartonellosis (disseminated only), blastomycosis, toxoplasmosis, coccidioidomycosis, histoplasmosis, aspergillosis (invasive only), candidiasis (invasive or pharyngeal), cryptococcosis, other invasive fungi (mucormycosis [zygomycosis, rhizopus, mucor, lichtheimia], scedosporium/pseudallescheria boydii, fusarium), legionellosis, listeria monocytogenes (invasive only), tuberculosis, nocardiosis, non-tuberculous mycobacterium, salmonellosis (invasive only), HBV reactivation, herpes simplex (invasive only), herpes zoster, strongyloides (hyperinfection syndrome and disseminated forms only), paracoccidioides, penicillium marneffei, sporothrix schenckii, cryptosporidium species (chronic only), microsporidiosis, leishmaniasis (visceral only), trypanosoma cruzi infection (Chagas' disease) (disseminated only), campylobacteriosis (invasive only), shigellosis (invasive only), vibriosis (invasive due to vibrio vulnificus), HCV progression [R17-2617].

# Potential Severe DILI

A potential severe Drug Induced Liver Injury (DILI) that requires follow-up is defined by any of the following alerts (alterations) of hepatic laboratory parameters:

- 1. Aspartate aminotransferase (AST) or alanine aminotransferase (ALT) elevation ≥3x ULN and total bilirubin (TBIL) ≥2x ULN measured at the same visit, or in samples drawn within 30 days of each other, OR
- 2. AST or ALT elevation  $\ge 3x$  ULN and INR  $\ge 1.5x$  ULN measured at the same visit, or in samples drawn within 30 days of each other, OR
- 3. AST or ALT elevation ≥3x ULN with new onset, or worsening of fatigue, nausea, vomiting, right upper quadrant pain or tenderness, fever, rash, and/or eosinophilia (>5%), OR
- 4. AST or ALT elevation  $\geq 5x$  ULN

# **Clinical Trial Protocol**

Page 87 of 177

Proprietary confidential information © 2023 Boehringer Ingelheim International GmbH or one or more of its affiliated companies

These laboratory findings constitute a hepatic injury alert, and participants showing any of these lab abnormalities need to be followed up according to the "DILI checklist" provided in the eDC system.

In case of clinical signs or symptoms of hepatic injury (icterus, unexplained encephalopathy, unexplained coagulopathy, right upper quadrant abdominal pain, etc.) without lab results (ALT, AST, TBIL) available, the investigator should make sure these parameters are analysed, if necessary, in an unscheduled blood test. Should the results meet the criteria of hepatic injury alert, the procedures described in the DILI checklist should be followed. Additionally, with participants having a normal AST and ALT at baseline, the emergence of an isolated AST or ALT elevation between ≥3-fold and <5x ULN requires repeat testing within 72 hours. DILI Checklist is not required unless repeat testing triggers alerts 1, 2, 3, or 4, mentioned above.

The following events should lead to immediate discontinuation of trial treatment (active or comparator):

- Hepatic injury alert numbers 1, 2, or 3
- Hepatic injury alert number 4, if persists >2 weeks
- AST or ALT elevation >8x ULN

Following completion of the DILI Checklist, if the BI investigational drug cannot be excluded as a possible cause of DILI event, then discontinuation should be made permanent without rechallenge. If an alternate causality, e.g. acute viral hepatitis, is confirmed by the DILI Checklist evaluation, then BI investigational drug may be re-started, if warranted.

# Peripheral neuropathy

Any event suspected or diagnosed as peripheral neuropathy would be considered as an AESI. For the treatment interruption rules, please see Section 3.3.4.1.

# 5.2.6.1.5 Intensity (severity) of AEs

The intensity (severity) of AEs should be classified and recorded in the CRF according to the CTCAE version 5.0.

# 5.2.6.1.6 Causal relationship of AEs

Medical judgement should be used to determine the relationship between the AE and the BI investigational compound, considering all relevant factors, including pattern of reaction, temporal relationship, de-challenge or re-challenge, confounding factors such as concomitant medication, concomitant diseases, and relevant history.

Arguments that may suggest that there is a reasonable possibility of a causal relationship could be as follows:

- The event is consistent with the known pharmacology of the trial drug.
- The event is known to be caused by or attributed to the drug class.
- A plausible time to onset of the event relative to the time of drug exposure.
- Evidence that the event is reproducible when the drug is re-introduced.

Page 88 of 177

Proprietary confidential information © 2023 Boehringer Ingelheim International GmbH or one or more of its affiliated companies

- No medically sound alternative aetiologies that could explain the event (e.g. pre-existing or concomitant diseases, or co-medications)
- The event is typically drug-related and infrequent in the general population not exposed to drugs (e.g. Stevens-Johnson syndrome)
- An indication of dose-response (i.e. greater effect size if the dose is increased, smaller effect size if dose is reduced)

Arguments that may suggest that there is no reasonable possibility of a causal relationship could be as follows:

- No plausible time to onset of the event relative to the time of drug exposure is evident (e.g. pre-treatment cases, diagnosis of cancer or chronic disease within days/weeks of drug administration; an allergic reaction weeks after discontinuation of the trial drug concerned)
- Continuation of the event despite the withdrawal of the medication, considering the pharmacological properties of the compound (e.g. after 5 half-lives); of note, this criterion may not be applicable to events whose time course is prolonged despite removing the original trigger
- There is an alternative explanation, e.g. situations where other drugs or underlying diseases appear to provide a more likely explanation for the observed event than the drug concerned
- Disappearance of the event even though the trial drug treatment continues or remains unchanged
- 5.2.6.2 Adverse event collection and reporting

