## Key pharmacokinetic and immunogenicity characteristics

Spesolimab has been characterised by typical IgG1 monoclonal antibody pharmacokinetics (PK). PK data showed that exposure increased with increasing dose in a dose proportional manner from 0.3 mg/kg to 20 mg/kg following intravenous (i.v.) administration of spesolimab to healthy volunteers. In healthy volunteers, the geometric mean spesolimab clearance (gCV%) was 0.146 (23.3%) L/day. The corresponding terminal half-life was 28.8 (25.1%) days. The clearance in GPP patients was approximately 25% higher.

Comparing the exposures between the 300 mg subcutaneous (s.c.) dose and 300 mg i.v. dose, a s.c. bioavailability of  $\sim$ 70% was determined. No differences in PK were observed between Caucasians and Japanese subjects.

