## Residual Effect Period (REP)

The REP of spesolimab is 16 weeks. This is the period after the last dose with measurable drug levels and/or pharmacodynamic effects still likely to be present.

c40061625-02 Clinical Trial Protocol

Page 28 of 177

Proprietary confidential information © 2023 Boehringer Ingelheim International GmbH or one or more of its affiliated companies

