#### **1.4.2** Risks

No other IL-36 receptor antagonist is currently approved, that would provide further information on identified risks in molecules of this class. The knowledge of the safety and risk profile of compounds in this class is still considered limited. However, the safety profile of spesolimab is considered acceptable based on available data from completed trials.

In order to protect the trial participant's safety during conduct of this trial, an independent Data Monitoring Committee (DMC) will periodically review clinical trial safety data. For details, please see Section 8.7. In addition to the AE tracking, planned interim analysis at of Part 1 of the trial will also contribute to the monitoring of any safety signal (see Section 7.2.8).

For potential risks, Table 1.4.2: 1 lists the possible risks for spesolimab as well as theoretical risks derived from general safety considerations of immunomodulatory drugs and from this trial specific procedures. For details on treatment-related risks, refer to Section 1.2 and IB [c03320877-11].

Page 32 of 177

Table 1.4.2: 1 Overview of trial-related and potential risks

Possible or known risks of clinical relevance for this trial	Summary of data, rationale for the risk	Mitigation strategy
Systemic hypersensitivity reaction	After administration of any biologic agent or protein, there is a possibility of occurrence of immediate (such as anaphylaxis) or delayed (such as drug reaction with eosinophilia and systemic symptoms) adverse immune reactions.	Patients with a history of allergy/hypersensitivity to the systemically administered trial medication agent or its excipients are excluded from the trial.  In case of systemic hypersensitivity reactions including anaphylactic reaction emerging during or after administration of trial medication, the investigator should consider in accordance with severity of the reaction and local standard of care to interrupt and treat the condition.
		Systemic hypersensitivity reaction is defined as an adverse event of special interest (AESI); see Section 5.2.6.1.4. It is subject to close monitoring and investigators are requested to assess these conditions using the criteria discussed in the statement paper from Sampson HA [R11-4890].

Page 33 of 177

Proprietary confidential information © 2023 Boehringer Ingelheim International GmbH or one or more of its affiliated companies

Table 1.4.2: 1 Overview of trial-related and potential risks (cont.)

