# 5.2.6.2.1 AE collection

The investigator shall maintain and keep detailed records of all AEs in the participant files.

Per default SAEs/AESIs should be reported via the eCRF in the EDC system. If the EDC system is not or no longer available (e.g. after database lock), the BI paper SAE form should be used; please see Section 5.2.6.2.2.

For trial participants not rolling over to LTE trial, the following must be collected and documented on the appropriate CRF(s) by the investigator:

- From signing the informed consent onwards until the individual participant's end of trial (usually the EoS visit, please see Section 6.2.3): all AEs (serious and non-serious) and all AESIs
- After the individual participant's end of trial: the investigator does not need to actively monitor the participant for new AEs but should only report any occurrence of cancer of new histology and trial drug-related SAEs and trial drug-related AESIs of which the investigator may become aware of by any means of communication, e.g. phone call; those AEs should be reported on the BI SAE form (see Section 5.2.6.2.2), but not on the CRF

For trial participants rolling over to LTE trial the following must be collected and documented on the appropriate CRF(s) by the investigator or delegated:

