The frequency of subjects with AEs will be summarized by treatment, primary system organ class and preferred term. AEs which were considered by the investigator to be drug related will be summarized separately. Separate tables will also be provided for subjects with SAEs, subjects with AEs leading to study drug discontinuation, subjects with AESIs, subjects with other significant AEs (derived based upon ICH E3 (9.9)), User-defined Adverse Event Concepts (UDAEC) (Table 7.8.1:1) and serious UDAEC. AEs will also be summarized by maximum intensity based on the CTCAE grading system.

For disclosure of AE data on ClinicalTrials.gov, the frequency of subjects with non-serious AEs occurring with an incidence of greater than 5% (in preferred terms) will be summarized by treatment, primary system organ class and preferred term. The frequency of subjects with SAEs will also be summarized.

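### The causality guide's example of a late allergic reaction conflicts with spesolimab's half-life and 16-week residual effect period, and could lead investigators to rate late hypersensitivity as unrelated

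*Protocol*

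**What the plan says.** Protocol 5.2.6.1.6 tells investigators how to judge relatedness. Its general instruction is: "Medical judgement should be used to determine the relationship between the AE and the BI investigational compound". Two lists follow, one for and one against a causal link. The second is introduced with: "Arguments that may suggest that there is no reasonable possibility of a causal relationship could be as follows". Its first item is onset timing that is implausible relative to exposure, and one of the examples is "an allergic reaction weeks after discontinuation of the trial drug concerned". The example carries no product-specific qualifier.

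Elsewhere the documents describe a drug that persists:

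- Protocol 1.2, pharmacokinetics (healthy volunteers): "The corresponding terminal half-life was 28.8 (25.1%) days". Clearance in patients with generalised pustular psoriasis was about 25% higher.
- Protocol 1.2, residual effect period (REP): 16 weeks. "This is the period after the last dose with measurable drug levels and/or pharmacodynamic effects still likely to be present".
- Protocol 7.2.6 and SAP 7.8.1: adverse events up to 16 weeks (112 days) after the last dose belong to the on-treatment period.
- Protocol Table 1.4.2: 1 names "immediate (such as anaphylaxis) or delayed (such as drug reaction with eosinophilia and systemic symptoms) adverse immune reactions" as a possible risk of any biologic. Section 4.2.1 sets out a work-up for suspected delayed hypersensitivity.

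Two places use the investigator's causality call directly. SAP 7.8.1 states: "AEs which were considered by the investigator to be drug related will be summarized separately". Protocol 5.2.6.2.1 limits what is reported after an individual's end of trial to new cancers and "trial drug-related SAEs and trial drug-related AESIs of which the investigator may become aware".

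**The concern.** The example treats a gap of weeks after stopping as evidence against the drug. For a compound cleared within days that would be reasonable. For spesolimab the same protocol treats those weeks as a time when drug or effect is likely to be present, and the analysis treats them as exposed time. The guide therefore points the other way from the pharmacology and from the analysis window.

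The event type matters as well. Systemic hypersensitivity is an adverse event of special interest (AESI), and Protocol 1.4.2 describes knowledge of the safety of this class as still limited. The only allergy example in the list against causality leans against one of the trial's named risks. At stake is the accuracy of the investigator-rated drug-related summary and, for a subset of participants, which events are reported after the trial.

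**Working it through.** The documents give no figure for the fraction of drug remaining, so there is nothing to reproduce. The check is simple first-order decay.

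**Inputs**
- Half-life 28.8 days, geometric CV 25.1% (Protocol 1.2, healthy volunteers). No value for hidradenitis suppurativa is visible.
- Clearance about 25% higher in another patient population (Protocol 1.2). With volume assumed unchanged, half-life = 28.8 / 1.25 = 23.04 days.
- REP 16 weeks = 112 days.

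**Formula:** fraction remaining = 0.5^(t / half-life).

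At 4 weeks: 0.5^(28/28.8) = 0.51. With the shorter half-life: 0.5^(28/23.04) = 0.43.

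| Time after last dose | Half-life 28.8 d | Half-life 23.04 d |
|---|---|---|
| 2 weeks | 71% | 66% |
| 4 weeks | 51% | 43% |
| 8 weeks | 26% | 19% |
| 16 weeks | 6.8% | 3.4% |

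**Between-subject range:** log-scale SD = sqrt(ln(1 + 0.251²)) = 0.247, so one geometric SD either side of 28.8 days gives 22.5 to 36.9 days. The 4-week fraction then runs from 42% to 59%. Nowhere in these ranges is drug exposure negligible a few weeks after the last dose.

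**What depends on the causality call**

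| Output | Depends on the investigator's causality rating? |
|---|---|
| Treatment-emergent events to last dose + 112 days (SAP 7.8.1) | No |
| AESI reporting to the sponsor (Protocol 5.2.6.1.4, 5.2.6.2.2) | No |
| Hypersensitivity and DRESS (drug reaction with eosinophilia and systemic symptoms) found by MedDRA search (SAP Table 7.8.1: 1) | No |
| Drug-related adverse event summary (SAP 7.8.1) | Yes |
| Reporting after the individual's end of trial (Protocol 5.2.6.2.1) | Yes, for serious events and AESIs |

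**When the last row applies.** For participants who do not roll over, all adverse events are collected regardless of cause until the individual's end of trial, usually the end-of-study (EoS) visit. Protocol Section 6 places that visit 112 days after the last dose or 98 days after the end-of-treatment visit, after the REP. Participants who roll over have everything collected until the first dose in the extension trial. The causality filter can therefore act inside the 16 weeks only when a trial ends early. Protocol 6.2.3 allows this, because it counts loss to follow-up and refusal of follow-up as trial completion.

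**The case against.** The strongest reply is that this is permissive guidance. The list offers arguments that may apply, under a general instruction to use medical judgement on all relevant factors, and the item itself refers to onset relative to exposure, which leaves room for persisting drug. An investigator who knows the half-life can disregard the example. That stands, and it reduces the claim to a risk. A reader might infer that drug-related hypersensitivity is in fact under-attributed; the documents do not show that, and the number of affected events is unknown.

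Three further inferences are tempting and should not be drawn.

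- **That the example removes events from post-trial reporting generally.** For anyone who completes follow-up the filter starts only after the REP, so only early endings are exposed to it.
- **That it removes events from serious-reaction reporting.** AESIs go to the sponsor on the expedited timeline whatever the attribution, and under Protocol 8.4 the sponsor makes its own causality and expectedness assessment.
- **That the list contradicts itself,** because the next item mentions 5 half-lives (5 × 28.8 = 144 days). That item concerns an event continuing after withdrawal, not the onset of a new one. The two criteria need not share a time limit.

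Nor can the decay figures be turned into a share of risk. That would require hypersensitivity risk to follow the amount of drug remaining, which the documents do not support.

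What the reply does not remove is the mismatch itself. Investigators apply their judgement with this list in front of them.

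**Conclusion.** The example is inconsistent with the protocol's own half-life, REP, on-treatment window and named delayed-reaction risk. That part is firm: about half the drug remains at 4 weeks (51%; 42% to 59% over one geometric SD; 43% with 25% higher clearance). It rests on first-order decay, a healthy-volunteer half-life and, for the 43%, an unchanged volume.

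The consequence is a possibility and a limited one. Late hypersensitivity within the REP could be rated unrelated. That would lower the drug-related summary, which is descriptive with no hypothesis test attached. For participants whose trial ends before the 112-day visit, it could also affect which serious events and AESIs are reported afterwards. The main safety counts are unaffected. This is a clarification worth making because it costs little and concerns a named risk; it does not threaten the trial's safety analysis.

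**What to change.** Reconcile Protocol 5.2.6.1.6 with Sections 1.2, 1.4.2, 4.2.1 and 7.2.6. Either delete the example or tie it to onset after the end of the REP. In both cases add a sentence saying that onset within 16 weeks of the last dose, including delayed reactions, is not by itself an argument against a causal relationship to spesolimab.

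Deletion is the more neutral choice. Tying the example to the end of the REP agrees with the protocol's own definition, but it keeps an argument against causality in the period when post-trial reporting depends on relatedness.

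The cost is a short text change in the next amendment and a line in site training. No dose, procedure or analysis changes. The downside is that slightly more events may be rated drug-related.
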